2.3.2 SAFETY RESULTS

A total of 12 patients were enrolled in this study. There were no SAEs reported.

In the 9 subjects analyzed on SCD treatment, no neutropenic events were reported. Mean WBC counts remained normal throughout treatment, with a mild decline noted upon initiation of therapy that was shown to rebound by day 7. No bleeding events were reported. Average platelet counts remained in the functional range (above 50,000) throughout treatment, with a mild decline noted upon initiation of therapy that was shown to plateau by day 4 to an average platelet count of 75,000. A summary of all adverse events (AEs) observed in the 9 subjects on SCD treatment is presented in **Table 2**. These events were not attributed to the

device by the investigator, as they commonly occur with CRRT treatment.

Table 2: Adverse event reporting – China Study – n=9 patients

Adverse Event (n=9 patients)	Number of Mild Severity Events	Number of Moderate Severity Events
Hypercalcemia	6	2
Thrombocytopenia	1	0
Hypocalcemia	0	1
Allergic Reaction	1	0
Hypophosphatemia	2	0
Hypernatremia	1	0

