6.4 STUDY OBSERVATION PERIOD

The Study Observation Period begins when the patient starts treatment and will continue up to a maximum of 168 hours from the time of Observation Start. **Patient will begin the Observation Period before the patient has reached 12 hours on CRRT.** A patient may begin CRRT therapy and SCD treatment at the same time, which would also mark the beginning of the Study Observation Period.

This observation period has been broken into seven 24 hour time periods. It ends when the patient has reached 168 hours in the observation period or when the patient meets the termination criteria outlined in **Section 7.2** as determined by the Principal Investigator or Medical Team at the participating Clinical Site.

All tests are scheduled on a 24 hour cycle, or once a day, and can be scheduled to be drawn around each participating site's ICU blood drawing schedule, with the exception of any test that requires a specific draw frequency.

The following information will be obtained for patients enrolled during the study observation period on a daily basis unless otherwise specified:

- **Vital Signs/Physical Assessment**
 - Temperature
 - Blood Pressure , heart rate
 - Urine Output (previous 24 hours)
 - Net Fluid Balance (previous 24 hours)
- **Clinical Laboratory Tests**
 - CBC with differential – every 12 hours (+/- 4 hours)
 - BUN, Creatinine
 - Na, K, Cl, HCO₃, Ca, ionized Ca, Mg, PO₄
 - ALT, AST, Bilirubin, ALP, Total Protein, Albumin, Glucose
 - PT, PTT, INR
- **Respiratory**
 - Status – Ventilator support (yes/no; date of extubation)
 - If on Vent: FiO₂
 - If on Vent with an arterial line: Arterial Blood Gas
 - If on Vent without an arterial line: Arterial Blood Gas (if available)
- **Blood for Research**
 - Collect at hours 48, 96, 144, and end of study (+/- 4 hours). If study observation period ends prior to hour 168, collect at end of study observation period. Blood for biomarkers will be collected as close as possible to the time of SCD scheduled changes in the days required (+/- 4 hours) if practical.
 - Blood sample will be sent to an outside laboratory for testing of biomarkers

- **CRRT Parameters (Start at hour 0)**
 - Parameters include modality, blood flow rate, net fluid removal, dialysate or replacement solution flow rate, citrate infusion rate, calcium replacement rate.
 - System performance (circuit survival - event driven)
 - Post filter ionized calcium (+/- 1 hour)

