Therapy Initiation	Q 1 hr. until post filter iCa level <0.40 mmol/L; then Q 6hr.
After any Calcium or Citrate rate change	Q 1 hr. until post filter iCa level <0.40 mmol/L; then Q 6hr.
After any Interruption: Recirculation, Procedure, Restart	Q 1 hr. until post filter iCa level <0.40 mmol/L; then Q 6hr.

- **SCD Performance (Start at hour 0)**
 - SCD [REDACTED] performance (event driven)
 - SCD and SCD Blood Tubing Set Change every 24 hour (+/-4 hour)
- **Other (Event Driven)**
 - Acknowledgement (yes/no) to critical medications administered to the patient
 - Adverse Events
 - Diagnostic/Therapeutic Procedures
 - Microbiology/culture data

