APPENDIX F – SCD-PED-01 Study Schedule of Events

	Baseline	Hr 0-24	Hr 25-48	Hr 49-72	Hr 73-96	Hr 97-120	Hr 121-144	Hr 145-168	Therapy End
Vital Signs/Physical Assessment									
Temperature , Body Weight (baseline only)	X	X	X	X	X	X	X	X	
Blood Pressure (if no bp, MAP acceptable), Heart Rate	X	X	X	X	X	X	X	X	
PRISM II Score	X								
Physical Exam	X								
Urine Output (previous 24 hours)	X	X	X	X	X	X	X	X	
Net Fluid Balance (previous 24 hours)		X	X	X	X	X	X	X	
Sepsis	X								
ICU Percent Fluid Overload at CRRT Initiation	X								
Clinical Laboratory Testing									
CBC with differential	X	q12h	q12h	q12h	q12h	q12h	q12h	q12h	
BUN/Creatinine	X	X	X	X	X	X	X	X	
Na, K, Cl, HCO ₃ , Ca, Mg, PO ₄ , Ionized Calcium	X	X	X	X	X	X	X	X	
ALT, AST, Bilirubin, ALP, TP, Albumin, Glucose	X	X	X	X	X	X	X	X	
PT, PTT, INR	X	X	X	X	X	X	X	X	
Urinalysis (if urine is available)	X								
Respiratory									
Arterial Blood Gas (pH, PaO ₂ , PaCO ₂) (if on vent)*	X	X	X	X	X	X	X	X	
Ventilator Settings (FiO ₂)	X	X	X	X	X	X	X	X	
Blood For Research									
Blood for Biomarkers	X		X(hr/48)		X(hr/96)		X(hr/144)		X
Extracorporeal Device Parameters									
CRRT (Settings- Event Driven)	X (hour 0)	X	X	X	X	X	X	X	
Post Filter Ionized Calcium	X (hour 0)	q1h until <0.40mmol/L; then q6h	q6h	q6h	q6h	q6h	q6h	q6h	
CRRT Device and SCD Performance (Event Driven)		X	X	X	X	X	X	X	
SCD 24hr. Daily Change		X	X	X	X	X	X	X	
Other (Event-Driven)									
Adverse Events	X	X	X	X	X	X	X	X	X
Critical Medications, Blood products (yes/no) per Appendix J	X	X	X	X	X	X	X	X	X
Diagnosis/Therapeutic Procedures	X	X	X	X	X	X	X	X	X
Microbiology/culture data	X	X	X	X	X	X	X	X	

*Required only if the presence of an A-line; see **Section 6.3** and **Section 6.4** for details

APPENDIX G – SCD-PED-01 Study Schedule of Events: Follow-up Period**Day 1 - 5 or until ICU discharge (whichever occurs first unless otherwise specified)**

Measurement	Hour 0 - 24	Hours 25 – 120 ¹
Vital Signs/Physical Assessment		
Blood pressure, temperature, and heart rate	X	X
Physical Exam	X	
Urine Output (from previous 24 hours)	X	X
Net Fluid Balance – (from previous 24 hours)	X	X
Clinical Laboratory Tests		
CBC with differential	X	
BUN/Creatinine	X	
Na, K, Cl, HCO ₃ , Ca, Mg, PO ₄ , Ionized Calcium	X	
Respiratory:		
Arterial Blood Gas (pH, PaO ₂ , PaCO ₂)	X	
Ventilator Settings (FiO ₂)	X	X
Other(event driven)		
Renal Replacement Therapy status	X	X
Microbiology/Culture Data	X	X
Adverse Events	X	X
Serious Adverse Event	X	X
Antibacterial Medications (yes/no)	X	X

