APPENDIX J – CRITICAL MEDICATION LIST

The following is a list of medication categories (with examples) to be acknowledged (yes/no) in the Case Report Forms if administered to the patient during the SCD-PED-01 Clinical Trial (starting at 24 hours prior to Observation until 168 hours of treatment or ICU discharge, whichever comes first. Only antibacterial use is captured during follow-up period.

ANTIBACTERIALS FOR SYSTEMIC USE

Ampicillin	Ceftazidime	Moxifloxacin
Azithromycin	Ciprofloxacin	Nafcillin
Aztreonam	Ciprofloxacin hydrochloride	Piperacillin
Bactrim (Sulfamethoxazole, Trimethoprim)	Clindamycin	Piperacillin w/tazobactam (Piperacillin, Tazobactam)
Cefadroxil	Daptomycin	Synercid (Dalfopristin,Quinupristin)
Cefalexin	Doripenem	Tigecycline
Cefazolin	Erythromycin	Tobramycin
Cefazolin sodium	Gentamicin	Vancomycin
Cefepime	Levofloxacin	
Cefepime hydrochloride	Linezolid	
Cefoxitin	Meropenem	
	Metronidazole	

ANTIMYCOTICS FOR SYSTEMIC USE

Amphotericin b, liposome	Fluconazole
Caspofungin	Micafungin

ANTITHROMBOTIC AGENTS

Acetylsalicylic acid	Clopidogrel	Enoxaparin sodium
Argatroban	Drotrecogin alfa	Heparin
Bivalirudin	Enoxaparin	Warfarin sodium

BLOOD SUBSTITUTES

Albumin	Albumin human	Blood, whole
Cryoprecipitate	Red blood cells	
Plasma	Red blood cells, leucocyte depleted	
Platelets		

VASOPRESSORS

Dobutamine	Norepinephrine	Phenylephrine hydrochloride
Dopamine	Norepinephrine bitartrate	Vasopressin
Epinephrine	Phenylephrine	
Milrinone		

APPENDIX K – CRRT PRESCRIPTION GUIDELINE and REGIONAL CITRATE ANTICOAGULATION (RCA) PROTOCOL EXAMPLE

1. **Purpose:** The purpose of the guidelines is to standardize, to the extent possible, the provision of CRRT to patients who require CRRT. While these guidelines should govern the CRRT prescription provided to most patients, there will be special circumstances (e.g. inborn errors of metabolism, exogenous toxin removal) that will require deviation from these guidelines.
2. **Modality:** CRRT will be prescribed as continuous veno-venous hemodiafiltration (CVVHDF). A total minimum small solute clearance of 2000 ml/min/1.73m² will be prescribed. The clearance will be divided equally between dialysis and hemofiltration as follows:
 - a. 50% as dialysis fluid using PrismaSateTM via the dialysis pump
 - b. 50% as replacement fluid divided between pre-replacement and post-replacement as follows:

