 - i. The initial and all new CRRT circuits will be not primed with blood but with crystalloid or other fluid that is the local standard of care.
 - ii. For daily SCD filter changes (not associated with a CRRT circuit change), a new crystalloid primed SCD will be placed in line with the CRRT circuit without need for blood priming.
 - iii. The investigator can prime with blood or other colloid if they believe it is clinically indicated.
- b) For patients >24-40 kg: The blood volume for this patient population is >1680-2800 ml, thus the SCD alone represents <10% of the patient blood volume, but the ECV of the SCD and any CRRT circuit will comprise >10% of the total patient blood volume. Thus, for patients >24 kg:
 - i. The initial and all new CRRT circuits will be primed with blood per the local standard of care protocol.
 - ii. For initial and daily SCD filter changes (not associated with a CRRT circuit change), a new crystalloid primed SCD will be placed in line with the CRRT circuit without need for blood priming.

- iii. The investigator can prime the SCD with blood or other colloid if they believe it is clinically indicated.
- c) For patients 15-24 kg: The blood volume for this population is <1680 ml, thus the HF1000 + SCD ECV represents >10% for the entire range of patient weight from 15-24 kg. Thus, for patients with a weight of 15-24 kg:
 - i. A crystalloid primed SCD circuit will be placed in line with a crystalloid primed CRRT circuit. For the initial CRRT/SCD circuit, the entire CRRT + SCD circuit will then be primed with blood per local standard of care prior to initiating CRRT /SCD therapy with the patient. Given the relatively large blood ECV to patient size in this group, the following patient lab parameters should be achieved prior to initiating CRRT/SCD therapy to prevent severe acidosis or hypocalcemia
 - a. Patient pH of at least 7.20
 - b. Patient ionized calcium of at least 1.1 mmol/L
 - ii. Patient should be given calcium gluconate IV (at least 300 mg) at the start of CRRT/SCD therapy.
 - a. An equivalent about of IV calcium can be given in a different formulation (ex. 100 mg of IV calcium chloride).
 - iii. Once the CRRT+SCD therapy is initiated, patient ionized calcium and pH should be obtained no later than 15 minutes after achievement of final CRRT blood flow and effluent rates.
 - iv. For the daily SCD circuit change, one of two options will be available:

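### Blood products are recorded only as a daily yes/no in one mixed category and circuit primes are not addressed, so platelet and haemoglobin changes cannot be adjusted for transfusion or prime dilution

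*Combined protocol and SAP*

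**What the plan says.** Appendix J describes a "list of medication categories (with examples) to be acknowledged (yes/no) in the Case Report Forms". One of its categories is headed "BLOOD SUBSTITUTES" and lists albumin, plasma, cryoprecipitate, platelets, red cells and whole blood. The row in Appendix F reads "Critical Medications, Blood products (yes/no) per Appendix J" and is marked at baseline, in each of the seven 24-hour treatment columns and at therapy end. After treatment, Appendix J states: "Only antibacterial use is captured during follow-up period".

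The complete blood count is taken every 12 hours (window 4 hours either way) during treatment (section 6.4) and again in the first 24 hours of follow-up (section 6.5.1, Appendix G). The device and its tubing are changed every 24 hours, with the same window.

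Appendix L sets the priming rules. For the smallest children, on the initial circuit, "the entire CRRT + SCD circuit will then be primed with blood per local standard of care". At each daily change in that group, the site may either repeat this with a new circuit or prime the new circuit with blood from the old one. In the middle weight band, the daily replacement device is primed with crystalloid unless the investigator prefers blood or colloid.

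**The concern.** Safety is the primary objective in the synopsis, and section 3.2 lists laboratory safety parameters among the safety measures. The blood count is sampled more often than the daily chemistry and coagulation panels. Platelets are a natural device-specific question: section 2.3.2 reports, in nine patients, a mild decline on starting therapy that was shown to "plateau by day 4 to an average platelet count of 75,000".

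Two routine events change a platelet or haemoglobin count without any action of the device on blood cells: transfusion, and mixing the child's blood with a prime. To allow for either, the analyst needs to know what was given, how much, and whether it came before or after the count. The yes/no supplies none of these. With up to 30 patients and no concurrent control arm, there is no comparison group in which these effects would cancel.

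**Working it through.** **Inputs (Appendix L).** Blood volume is 70 ml/kg. The device holds 120 ml. The HF1000 circuit holds 165 ml. The HF1200 circuit holds 83 + 156 = 239 ml.

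**Reproducing the plan's figures.**
- HF1000 plus device: 165 + 120 = 285 ml, as stated. The weight at which this is 10% of blood volume is 285/(0.10 × 70) = 40.7 kg (stated 40). For the circuit alone it is 165/7 = 23.6 kg (stated 24).
- HF1200 plus device: 239 + 120 = 359 ml, as stated. The cut-offs are 359/7 = 51.3 kg (stated 51) and 239/7 = 34.1 kg (stated 34).

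The volumes and weight bands agree, so they can be used for dilution.

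**One full prime.** If the prime carries no platelets (an assumption; the documents do not give its content), the fractional fall is V/(blood volume + V).

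| Weight | Blood volume | 285 ml prime | 359 ml prime |
|---|---|---|---|
| 15 kg | 1,050 ml | 285/1,335 = 21.3% | 359/1,409 = 25.5% |
| 24 kg | 1,680 ml | 285/1,965 = 14.5% | 359/2,039 = 17.6% |

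**Repetition.** If all six later daily changes also used a new blood-primed circuit, a 15 kg child would receive 7 × 285 = 1,995 ml to 7 × 359 = 2,513 ml of prime, or 1.9 to 2.4 blood volumes. A circuit-to-circuit prime adds no new donor prime. The two options therefore give very different dilution, and no section asks which was used.

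**Crystalloid device changes.** One 120 ml crystalloid prime lowers the count by 120/1,800 = 6.7% at 24 kg and 120/2,920 = 4.1% at 40 kg. As an upper bound, suppose the blood in the old device is discarded and no platelets are regenerated. Six changes with the HF1000 circuit then give 1 − (1 − 120/1,965)^6 = 31.5% at 24 kg and 1 − (1 − 120/3,085)^6 = 21.2% at 40 kg. Crystalloid primes therefore need recording as well as blood primes.

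**Haemoglobin.** A crystalloid prime lowers haemoglobin by the same fraction. For a blood prime the effect depends on the haemoglobin of the prime, which the documents do not give, so no figure is offered.

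**Timing.** Each 24-hour column holds 24/12 = 2 blood counts. A single yes does not show whether the product came before the first count, between the two, or after the second. It also does not separate platelets from albumin. Only the biomarker samples are tied to the device change; the blood count is not.

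**Primes.** Appendix J covers products given to the patient. No section says whether blood used to prime a circuit should be ticked.

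**End of capture.** The first follow-up blood count falls after blood-product recording has stopped.

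**The case against.** A reader might infer that transfusions go unrecorded, that a fall caused by the device would be hidden, and that the counts cannot show what the device did. The documents do not support this, for four reasons.

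- Use is flagged in every 24-hour column, so windows marked no can be analysed separately, provided sites count primes.
- Section 9.1 makes a new or worsening clinically significant laboratory abnormality an adverse event and names thrombocytopenia. Section 9.7 says expected intensive-care findings must still be reported, and section 9.5 requires a causality assessment.
- With 12-hourly sampling, a platelet count low enough to prompt transfusion would usually itself be in the data, so the nadir would often survive.
- The documents give no transfusion trigger, dose or expected rise, so any figure for the share of falls masked would rest on assumed inputs alone.

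A reader might also infer that primes are captured as a yes/no. The documents are silent on this, which is a separate gap.

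Other points have force. The 21.3% to 25.5% range is the lightest-child extreme. With the HF1000, children above 40 kg need no blood prime. Prime volume can be partly reconstructed from weight, hemofilter, the Appendix L rules and change events. Stopping for thrombocytopenia under section 7.3 is a bedside judgement made with the chart to hand, and the case report form does not affect it. Attribution is limited in any case without concurrent controls, and the case report form itself is not among the documents and may hold more.

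What remains is that both appendices specify yes/no. Reconstruction fails where priming is left to the investigator or to local practice, and nothing recorded places a platelet transfusion before or after a given count.

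**Conclusion.** The point holds as a weakness in data capture. As specified, changes in platelet and haemoglobin counts cannot be adjusted for transfusion or prime dilution, although they remain partly informative. Assuming a platelet-free prime and the protocol's own volumes, one full prime alone lowers the platelet count by 21.3% to 25.5% at 15 kg and by 14.5% to 17.6% at 24 kg. Whether the effect recurs depends on a priming choice that the documents do not ask sites to record. The size of any masking by transfusion cannot be derived from the documents. This does not invalidate the safety assessment. It is an inexpensive improvement that should be made, and it is best made prospectively.

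**What to change.** In Appendices F and J, with matching text in sections 6.3, 6.4 and 6.5.1 and Appendix G:

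- Replace the yes/no for blood products with product type, volume and date/time.
- At each circuit or device change, record prime type (blood, colloid, crystalloid or circuit-to-circuit) and volume.
- Collect both from baseline through the first follow-up blood count.

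In the analysis:

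- Report the platelet nadir together with the number of platelet-transfusion days.
- Mark each count as before or after a platelet transfusion.
- Show the trajectory alongside the dilution expected from the recorded prime volumes.

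Do not simply drop counts taken within 24 hours of a blood prime. In children given a new blood-primed circuit daily, that would remove nearly every count, and it would miss the crystalloid device changes in larger children.

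The cost is a form change and modest transcription from existing charts for up to 30 patients. No procedure or clinical rule changes.

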5. SELECTION OF PATIENT POPULATION

5.1 STUDY POPULATION

Up to 30 pediatric patients will be enrolled in this study, in up to 10 Clinical Centers in the United States.

Pediatric patients with a body weight (BW) greater than or equal to 15 kg receiving care in the Intensive Care Units of each participating hospital will be screened daily and identified for participation in the trial. See **Appendix E**, CRRT Management.

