5.3 EXCLUSION CRITERIA

1. Threshold blood pressure of 80/40 mmHg-- patients with both a systolic blood pressure of less than 80 mmHg and a diastolic blood pressure of less than 40 mmHg.
2. Irreversible brain damage based on available historical and clinical information.
3. Patients with a solid organ transplant or those with a bone marrow or stem cell transplant in the previous 100 days or who have not engrafted.
4. Acute or chronic use of circulatory support device, other than ECMO, such as LVADs, RVADs, BIVADs.
5. Presence of preexisting advanced chronic renal failure (i.e., ESRD) requiring chronic renal replacement therapy prior to this episode of acute kidney injury or with pre-existing chronic kidney disease (CKD) defined as a eGFR <30 ml/min/1.73m 2 . Patients who have never seen a pediatric nephrologist will be assumed not to have pre-existing CKD.
6. AKI occurring in the setting of burns, obstructive uropathy, vasculitis, scleroderma renal crisis, atheroembolism, functional or surgical nephrectomy, cyclosporine or tacrolimus nephrotoxicity.
7. Received >12 hour of CRRT (not including SCUF on ECMO) during this hospital admission or prior to transfer from an outside hospital.
8. Received >1 hemodialysis treatment during this hospital admission or prior to transfer from an outside hospital.
9. Metastatic malignancy which is actively being treated or may be treated by chemotherapy or radiation during the subsequent three month period after study therapy.
10. Chronic immunosuppression with the exception of corticosteroids up to a dose of 10 mg per day.
11. HIV or AIDS.
12. Severe chronic liver failure as determined by standard diagnostic requirements.

13. Current Do not Attempt Resuscitation (DNAR), Allow Natural Death (AND), or withdrawal of care status, or anticipated change in status within the next 7 days.
14. Patient not expected to survive 28 days because of an irreversible medical condition. (This is not restrictive to AKI, and may include situations such as the presence of irreversible brain damage, untreatable malignancy, inoperable life threatening condition, or any condition to which therapy is regarded as futile by the PI.)
15. Any medical condition that the Investigator thinks may interfere with the study objectives.
16. Physician refusal.
17. Dry weight <15 kg.
18. Platelet count <15,000/mm³.

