6.2.2 BLOOD CIRCUIT VOLUME

The additional blood volume for the SCD is 120 ml. This additional circuit blood volume for the standard SCD in >20 kg patients can be handled with blood priming with matched blood similar to the standard practice in neonates. Blood prime will occur if the total extracorporeal circuit volume (ECV) is greater than 10% of the patient's blood volume, based on an estimate of blood volume = 70 ml/kg x patient body weight (kg) [24]. The situation is most commonly encountered in neonatal CRRT, where circuit ECV can represent nearly 50% of patient blood volume, yet the same principles apply for this clinical study. [25]

Hypotension associated with blood priming can occur from transient dilution of vasoactive medications (e.g., norepinephrine), or from exposure to the hyperkalemic, hypocalcemic acidotic nature of blood banked blood, which can cause a bradykinin release syndrome (BRS) when the blood is exposed to the CRRT membrane. The BRS is usually associated with AN-69 membranes that will not be used in this study. Each center has its own blood priming protocol to mitigate the potential for this reaction. However, minimum standards for blood priming in this trial are detailed in Appendix L to ensure patient safety. [26]

Patients with AKI requiring CRRT are often hypotensive prior to initiation of CRRT. Initiation of CRRT itself can improve hemodynamics by correcting acidosis and hypocalcemia. Most patients with hemodynamic instability receive vasoactive medications. Since the age range and associated normal blood pressure parameters is wide for this pediatric study, it is difficult to mandate an age specific lower blood pressure threshold to preclude CRRT initiation, especially if CRRT can address the instability as noted above. However, a threshold BP of 80/40 mmHg-- patients with both a systolic blood pressure of less than 80 mmHg and a diastolic blood pressure of less than 40 mmHg will not be entered into the study.

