- iii. Patient ionCa managed by CaCl₂ rate
 1. For patient ionCa < 0.9, increase CaCl₂ 20%
 2. For patient ionCa 0.9- 1, increase CaCl₂ 10%

3. For patient ion Ca 1.3-1.5, decrease CaCl₂ 10%
4. For patient ion Ca > 1.5, decrease CaCl₂ 20%

- 4. Access Size: (per clinical investigator decision)**
- 5. Blood pump flow rate: The minimum blood pump flow rate should be 50 ml/minute to prevent circuit clotting unless not clinically tolerated:**
 - a. Neonate/Infants – 8 to 12 ml/kg/minute
 - b. Toddlers – 6 to 8 ml/kg/minute
 - c. Older children and adolescents – 3-6 ml/kg/minute
- 6. 3-hour Fluid Balance Safety Limit: Limits set to prevent < 5% of blood volume error over 3 hours for smaller patients and < 10% over three hours for larger patients**
 - a. Patients < 30 kg – 150 ml
 - b. Patients 30-50 kg – 200 ml
 - c. Patients > 50 kg – 300 ml
- 7. Scheduled circuit changes: Circuits should be changed no later than every 72 hours, as this is the maximum interval at which the machine has been tested by the manufacturer for accuracy. Any diversion from this recommendation must have rationale documented in the medical record. The following situations serve as examples:**
 - a. The patient has a do not resuscitate or do not escalate care order that was placed on the chart while the patient is receiving CRRT.
 - b. The patient is so clinically unstable that the patient will likely not tolerate stopping and restarting CRRT.
- 8. Blood priming at CRRT initiation and blood return at CRRT termination**
 - a. Blood priming of the CRRT circuit should be done if the extracorporeal volume of the circuit is > 10% of the patient's blood volume.
 - b. Blood should not be returned to the patient at CRRT termination when circuits are blood primed unless specifically requested by the physician in a separate order.

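### Appendix K's 150 ml three-hour fluid balance limit for patients under 30 kg is 7 to 14% of blood volume at the protocol's own 70 ml/kg, not the stated 5%

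*Combined protocol and SAP*

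**What the plan says.** Appendix K, item 6, gives a reason for its limits and then the limits themselves. The reason is: "Limits set to prevent < 5% of blood volume error over 3 hours for smaller patients", with a corresponding 10%, also over three hours, for larger patients. The limits follow in three weight rows: "Patients < 30 kg – 150 ml", "Patients 30-50 kg – 200 ml" and "Patients > 50 kg – 300 ml". The item does not say which rows count as smaller and which as larger.

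Two other parts of the protocol supply what is needed to check the percentages. Section 6.2.2 and Appendix L both estimate blood volume as 70 ml per kg of body weight. Section 5.1 describes the population as "Pediatric patients with a body weight (BW) greater than or equal to 15 kg", and Section 5.3 excludes "Dry weight <15 kg". Eligible patients in the lowest row therefore weigh from 15 kg to just under 30 kg.

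On status, Section 6.2.1 has each site follow its own regional citrate protocol and offers Appendix K as an example that sites may use. Appendix E leaves ultrafiltration and the fluid prescriptions to the investigator and treating team. Item 1 of Appendix K says that its guidelines should govern most prescriptions, but that binds only a site that has adopted the example.

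**The concern.** A percentage of blood volume and a volume in millilitres are two statements of the same limit, linked by weight. A fixed volume over a wide weight range is largest, as a share of blood volume, at the bottom of the range. The lowest row spans a factor of two in weight and carries the stricter percentage, so it is where a mismatch would be expected.

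What is at stake is how a safety margin is understood. A site that adopts the example and reads the 5% as describing its under-30 kg patients would take the margin to be tighter than the volume allows. The quantity is not trivial on the protocol's own scale: at 15 kg, 150 ml is 150 / 15 = 10 ml/kg, the same volume per kg as the fluid bolus that Section 6.2.2 specifies for hypotension at circuit initiation. Safety is the primary objective, and hemodynamic variables are among the safety measures.

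**Working it through.** **Inputs.** Limits of 150, 200 and 300 ml, and percentages of 5 and 10 over three hours (Appendix K, item 6). Blood volume of 70 ml/kg (Section 6.2.2, Appendix L). Minimum weight of 15 kg (Sections 5.1 and 5.3).

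**Formula.** Share of blood volume = limit / (70 × weight).

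**Step 1: try to reproduce the stated 5% in the under-30 kg row (150 ml).**

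| Weight | Blood volume | Share |
|---|---|---|
| 15 kg | 1050 ml | 150/1050 = 14.3% |
| 20 kg | 1400 ml | 150/1400 = 10.7% |
| 24 kg | 1680 ml | 150/1680 = 8.9% |
| just under 30 kg | about 2100 ml | 150/2100 = 7.1% |

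The 5% is not reproduced at any eligible weight in the row. 150 ml falls to 5% at 150 / (0.05 × 70) = 42.9 kg, outside the row, and to 10% at 150 / (0.10 × 70) = 21.4 kg. As a measure of the gap only, 5% of blood volume is 52.5 ml at 15 kg and 105 ml at 30 kg. At 15 kg the limit is thus 150 / 52.5 = 2.9 times the stated share.

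**Step 2: check the 10% in the other rows.**

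- 30-50 kg, 200 ml: 200/2100 = 9.5% at 30 kg, falling to 200/3500 = 5.7% at 50 kg.
- Over 50 kg, 300 ml: below 300/3500 = 8.6%.

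Both rows are within 10%. If the 30-50 kg row were meant to count as smaller, it would miss the 5% too, since 200 ml is 5% only at 200 / (0.05 × 70) = 57.1 kg.

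**Step 3: look for a reading that restores the 5%.**

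- *A different blood volume.* At an assumed 80 ml/kg the row still runs from 150/1200 = 12.5% to 150/2400 = 6.3%. To reach 5% would take 150 / (0.05 × 30) = 100 ml/kg at 30 kg and 150 / (0.05 × 15) = 200 ml/kg at 15 kg.
- *An hourly limit.* 150 ml spread over three hours is 50 ml per hour, or 4.8% at 15 kg and 2.4% at 30 kg. That would fit, but the item specifies three hours for both percentages. On an hourly basis the upper rows would be at most 200/3/2100 = 3.2%, far from 10%, whereas on the three-hour basis they peak at 9.5% and 8.6%.
- *The two percentages exchanged.* Children of 15 to 21.4 kg would still exceed 10%, and 300 ml exceeds 5% up to 300 / (0.05 × 70) = 85.7 kg.

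**Step 4: the wording.** Taken literally, the sentence says that errors smaller than 5% are what the limits prevent. The evident intention is to prevent errors of 5% or more.

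**The case against.** The strongest reply is that the item has little reach. It sits in an optional example, and its operative content is the volume for each weight row, which is unambiguous; the percentage is an explanation. No eligibility rule, endpoint or analysis uses either figure. The protocol does not say what happens when the limit is reached. All of this stands, and it lowers the priority of the point. It does not make the two figures agree.

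Four stronger readings are tempting, and the documents do not support them:

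- *The plan guarantees 5%.* The item states what the limits were set for. It gives no assurance, and the limit is a ceiling, not an expected error.
- *The whole table contradicts its percentages.* Only the pairing of 5% with 150 ml fails if smaller patients are those under 30 kg. The two upper rows are consistent with 10%.
- *Every child under 30 kg has a looser relative limit than any heavier child.* The maximum at 30 kg or above is 9.5%, and 150 ml exceeds that share only below 30 × 150/200 = 22.5 kg.
- *Volume events in small children would be mistaken for device effects.* Nothing in the text shows this. Net fluid balance is recorded daily, Section 6.2.2 handles hypotension at initiation, and Section 9.5 requires causality to be judged against concurrent disease and procedures.

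**Conclusion.** The inconsistency is real and narrow. In the under-30 kg row the three-hour limit is 14.3% of blood volume at the lightest eligible weight and 7.1% at the top of the row, against a stated 5%. Every eligible child in the row is above 5%, and those below 21.4 kg are also above the 10% given for larger patients.

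This rests on the protocol's 70 ml/kg, its 15 kg minimum weight, and the natural reading that smaller patients are those in the lowest row. The conclusion is not sensitive to the blood volume figure within any plausible range.

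It should be corrected, but it is not a must-fix: only sites that adopt the Appendix K example are affected, and no endpoint or analysis depends on it.

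**What to change.** The sponsor's clinical team should make three changes to Appendix K, item 6:

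1. Reconcile the stated 5% with the 150 ml limit for the under-30 kg row, using the protocol's 70 ml/kg. Whether the percentage or the volume changes is for the clinical team to decide; this review takes no position.
2. Define smaller and larger patients by naming the weight rows that each percentage covers.
3. Reword the opening sentence so that it no longer says the reverse of what is intended.

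The cost is an edit to one appendix item. Either the stated percentage becomes less favourable for small children or the limit for that row changes. Sites that have already adopted the example would need to be told.
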